#### 15.2.1 Analysis Populations

# 15.2.1.1 Screened Population

The Screened Population will include all subjects who signed the informed consent form and are screened for participation in this study. This set will be used only for the purpose of describing subject disposition.

## 15.2.1.2 Safety Population/Intent-to-Treat (ITT) Population

The Safety Population will include all subjects who receive at least one dose of study medication. The ITT Population will be identical to the Safety Population for this study. All baseline characteristics, demographic and efficacy endpoint data will be presented using the ITT Population.

# 15.2.1.3 Pharmacokinetic (PK) Population

The PK Population will include all subjects in the Safety Population who have at least one evaluable post-dose PK measurement.

# 15.2.1.4 Pharmacodynamic (PD) Population

The PD Population will include all subjects in the Safety Population who have at least one evaluable post-dose PD measurement.

# 15.2.1.5 Data Review for Analysis Populations

After all the data have been verified/coded/entered into the database, a review will be performed. The purpose of this review will be to define the analysis populations. The review will also check the quality of the data, identifying outliers, and making decisions on how to deal with problems in any data (e.g., missing values, withdrawals, protocol deviations). After the

pre-analysis review, resolution of all issues and documentation of all decisions, the database will be locked.

# 15.2.2 Safety Analyses

All safety endpoints will be evaluated using the Safety Population.

#### 15.2.2.1 Adverse Events

Treatment emergent adverse events are defined as those AEs that develop or worsen after the first dose of study medication and up to 30 days beyond the last dose of study medication. The current version of MedDRA will be used to classify all AEs.

A by-subject TEAE data listing, including verbatim term, preferred term, treatment, severity, and investigator judgment of relationship to treatment, will be provided. The number of subjects reporting each preferred term within each system organ class will be tabulated by cohort and dose group. Tabulations will be produced for all TEAEs and for those considered potentially treatment related (causality to study drug is reported as possibly or probably, or where causality is not reported). The number of TEAEs will also be presented including both the total number of TEAEs and the total number of unique TEAEs (counting only unique terms within each subject).

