#### 14. ADVERSE EVENTS

#### 14.1 Definition

An adverse event (AE) is any untoward medical occurrence associated with the use of a drug in humans, whether or not considered drug related. An AE can therefore be any unfavorable and unintended sign, including a clinically significant abnormal laboratory finding, symptom, or disease temporally associated with the use of a study drug, whether or not considered related to the study drug (United States Food and Drug Administration (FDA) guidance, December 2012). Any abnormal laboratory finding that is deemed not clinically significant is not an AE.

Adverse events include the onset of new illness and the exacerbation of pre-existing conditions. Any medical condition that is present at the time that the subject is screened should be recorded on the medical history eCRF and not reported as an AE. However, if that condition deteriorates or severity changes at any time during the study, it should be recorded as an AE.

Any AEs that occur prior to dosing on Day 1 will be categorized as pre-treatment events. TEAEs will be defined as those AEs that occur after dosing on Day 1, or worsen in severity, and up to 30 days after the last dose of APL-2.

A suspected adverse reaction means any AE for which there is a reasonable possibility that the drug caused the AE. Reasonable possibility means there is evidence to suggest a causal relationship between the drug and the AE.

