## 5.2.1 Adverse Events

TEAEs are defined as those AEs that occur after Dosing on Day 1, or worsen in severity, and up to 30 days after the last dose of APL-2. For subjects who rollover to Part B long term extension phase, any AE recorded on the date of Visit 15 (start of dosing for the extension phase) will be included in Part A. Version 20.0 of MedDRA will be used to classify all AEs.

AEs will be considered treatment-emergent (TEAE) unless there is clear indication that the event occurred prior to first dose of study drug. AEs present prior to the first dose of study drug administration that increased in severity or relationship to study drug after the first dose of study drug and up to 30 days beyond the last dose of study drug will be classed as a TEAE. Events with missing or partial dates will be handled such that in the absence of contradictory information an AE is treatment emergent. So, for a missing start date (where stop date is after date of first dose) the date will be imputed as the date of first dose; for a missing stop date the date will be imputed as the last study date. If a partial date is recorded, the following convention will be used to assign the AE:

If a start date is missing the day information and month/year is the

same as first dose date then use first dose date, else '01' will be used for the day; if a start date is missing the month and the year is the same as first dose date then use first dose date, else January will be used for the start month.

• If a stop date is missing the day information and month/year is same as last study date then use last study date, else last day of the given month will be used for the stop day; if a stop date is missing the month and year is the same as last study date then use last study date, else December will be used for the stop month.

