#### Version 1.0

#### 5.2.1 Adverse Events

#### 5.2.1.1 Treatment-Emergent Adverse Events (TEAE)

TEAEs are defined as those AEs that occur after Dosing on Day 1, or worsen in severity, and up to 8 weeks (56 days) after the last dose of APL-2.

AEs will be considered Treatment-Emergent (TEAE) unless there is clear indication that the event occurred prior to first dose of study drug. AEs present prior to the first dose of study drug administration that increased in severity or relationship to study drug after the first dose of study drug and up to 56 days beyond the last dose of study drug will be classed as a TEAE. Events with missing or partial dates will be handled such that in the absence of contradictory information an AE is Treatment-Emergent. So, for a missing start date (where stop date is after date of first dose) the date will be imputed as the date of first dose; for a missing stop date the date will be imputed as the last study date. If a partial date is recorded, the following convention will be used to assign the AE:

- If a start date is missing the day information and month/year is the same as first dose date then use first dose date, else '01' will be used for the day; if a start date is missing the month and the year is the same as first dose date then use first dose date, else January will be used for the start month.
- If a stop date is missing the day information and month/year is same as last study date then use last study date, else last day of the given month will be used for the stop day; if a stop date is missing the month and year is the same as last study date then use last study date, else December will be used for the stop month.

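### Part A SAP 5.2.1 lets an adverse event that began before the first dose become treatment-emergent on a raised causality rating alone, against Protocol 14.1; the Part B SAP repeats the clause but contradicts it in the next subsection

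*Protocol*

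**What the plan says.** Protocol 14.1 gives two rules. Events before the first dose have their own class: "Any AEs that occur prior to dosing on Day 1 will be categorized as pre-treatment events". The treatment-emergent class, with a window counted from the final dose, is then set out: "TEAEs will be defined as those AEs that occur after dosing on Day 1, or worsen in severity, and up to 30 days". Protocol 14.4 repeats the pre-treatment rule. Protocol 15.2.2.1, in the statistics section, words the definition more loosely: "Treatment emergent adverse events are defined as those AEs that develop or worsen after the first dose of study medication". None of these makes a change in causality a criterion.

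Part A SAP 5.2.1 opens in line with Protocol 14.1, with the same window: "TEAEs are defined as those AEs that occur after Dosing on Day 1, or worsen in severity, and up to 30 days". Its next paragraph extends the class to events already present at baseline, on this condition: "increased in severity or relationship to study drug after the first dose of study drug and up to 30 days". Part B SAP 5.2.1.1 has the same two-step structure with a longer window, and its extension reads: "increased in severity or relationship to study drug after the first dose of study drug and up to 56 days".

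Part B SAP 5.2.1.2 then defines what is summarised. The Part A + B tables take TEAEs that start on or after the first APL-2 dose, and the Part B tables take those that start on or after the first 1,080 mg dose. The Part A SAP has no equivalent rule.

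**The concern.** A new causality opinion is not a clinical change. An event that began before any APL-2 and stayed at the same severity did not emerge on treatment, yet under the Part A SAP a revised rating is enough to make it a TEAE. The incidence and severity of TEAEs are the primary endpoint, and the trial is open-label.

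Events with onset before dosing are plausible here. Adverse events are collected from consent (Protocol 14.2, 14.4). Missing vaccinations may be given up to Day 1 (Protocol 12.2). Subjects on erythromycin or azithromycin start it at least a week before APL-2 (Protocol 11.4.1, 12.1).

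An increase in relationship is also not fully defined. The scale in Protocol 14.4.1 includes an Unknown category with no rank, and the overall summary in Part B SAP 5.2.1.6 counts Unknown as related.

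**Working it through.** The plan gives no figure to reproduce: Protocol 15.1 states that the sample size rests on no formal calculation. The check compares the texts and then works out the weight of one subject.

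**1. Definitions side by side**

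| Source | What makes an AE treatment-emergent | Can causality alone do it? |
|---|---|---|
| Protocol 14.1 | Onset after Day 1 dosing, or worse severity | No |
| Protocol 15.2.2.1 | Onset or worsening after the first dose | No |
| Part A SAP 5.2.1, opening sentence | As Protocol 14.1 | No |
| Part A SAP 5.2.1, next paragraph | Pre-dose AE with a rise in severity or in relationship | Yes |
| Part B SAP 5.2.1.1, opening sentence | As Protocol 14.1, with a 56-day window | No |
| Part B SAP 5.2.1.1, next paragraph | As Part A, with a 56-day window | Yes |

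Each SAP departs from Protocol 14.1 and from its own opening sentence.

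**2. Precedence.** Section 2 of each SAP lets it override the protocol's statistical section. That settles the difference from Protocol 15.2.2.1. It does not reach Section 14, and it cannot settle a contradiction within a SAP.

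**3. Path through the Part A SAP.** Take an AE that starts in screening, never worsens, and is rated more closely related after dosing begins.
- 5.2.1 flags it as a TEAE.
- 4.5 treats Part A as running from screening to Day 336. For subjects who roll over it keeps AEs that start up to Visit 15, with no lower limit; for the others it keeps all data.
- The Adverse Events Summary under 5.2.1 assigns AEs to the part in which they began, and tabulates by the TEAE flag.

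Nothing removes the event, so it can reach the TEAE tables.

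**4. Path to the related tables.** The related-TEAE tables by system organ class and preferred term need a rating of at least possibly related. A move from not related to unlikely related changes only the all-TEAE tables.

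**5. Weight of one subject.** Protocol 11.3.2 plans 6 per dose group and 12 per cohort, 24 in all. One extra subject in a row adds 100/n points:
- n = 6: 100/6 = 16.7
- n = 12: 100/12 = 8.3
- n = 24: 100/24 = 4.2

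The row for any TEAE moves only if that subject has no other TEAE.

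**6. Path through the Part B SAP.** 5.2.1.1 flags the same event as a TEAE, but the start-date rule in 5.2.1.2 keeps it out of both sets of summaries. The same rule drops a pre-dose AE that worsened in severity after dosing, if it keeps its original start date; Protocol 14.1 and 15.2.2.1 both count that event.

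The time-to-onset formula in 5.2.1.4 also assumes onset on or after the first dose. It is onset date minus first-dose date plus 1:
- onset 1 day before: -1 + 1 = 0
- onset 10 days before: -10 + 1 = -9
- onset 30 days before: -30 + 1 = -29

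Zero or negative time at risk has no meaning. The formula therefore fits 5.2.1.2 and not 5.2.1.1.

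**The case against.** A reader might infer that both SAPs carry pre-treatment events into the primary endpoint. The documents do not support that for the Part B SAP, because 5.2.1.2 screens its summaries by start date.

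A reader might also infer that a re-rated pre-dose event goes straight into the related tables. Protocol 14.4.1 makes this unlikely: a possible relationship requires a reasonable time relation to drug intake, and an unreasonable one points to not related. An unchanged event that predates the drug would not normally qualify. The route is narrow, though Unknown remains a gap where it is counted as related.

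Other points on this side are fair. The trial is a descriptive pilot with no formal inference. The error runs towards over-counting harm, which some would call conservative. The listings show all AEs with relationship and start day relative to dosing, so a pre-dose onset stays visible. No document shows that any event was re-rated.

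These points limit the size of the problem but do not remove it. The clause is a stated rule for the primary endpoint and conflicts with the protocol's definition. Neither SAP identifies or justifies it as a departure, and a listing does not correct a table count.

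**Conclusion.** The inconsistency is real in both SAPs, but it can change table counts only under the Part A SAP. There it can add pre-treatment events to the TEAE tables and, through a narrow route, to the related-TEAE tables. Each affected subject is worth 16.7 points in a row for a dose group of 6 or 8.3 points for a cohort of 12. This assumes that the planned numbers are reached and that the subject is not already in that row. The number of affected subjects cannot be derived from the documents and is probably low, so a material inflation of overall TEAE incidence should not be inferred.

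In the Part B SAP the defect is the contradiction between 5.2.1.1 and 5.2.1.2. Its practical effect is the reverse: pre-dose events that worsened in severity are left out although the protocol counts them. This assumes that a worsening is not entered as a new record with its own start date, a point the documents do not settle. The planned denominators do not carry over either, because the Part B Safety Set holds only subjects who rolled over and received at least one 1,080 mg dose.

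The point merits correction because it touches the primary endpoint and is cheap to fix.

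**What to change.** - In Part A SAP 5.2.1 and Part B SAP 5.2.1.1, delete relationship to study drug as a trigger, so that a pre-dose AE becomes a TEAE only if its severity increases after the first dose.
- Keep re-rated pre-dose AEs in the all-AE listing, labelled as pre-treatment events, with the latest causality rating.
- Amend Part B SAP 5.2.1.2 to include pre-dose AEs that worsened in severity, dated from the worsening. This agrees with 5.2.1.1 and gives the formula in 5.2.1.4 a usable onset date.
- Part B SAP Section 2 says that SAP Version 1.0 was used to produce the interim Part A analysis. Where those tables stand, report the departure and the number of affected subjects in the study report; Section 2 of each SAP already requires deviations to be discussed there.

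The cost is a small edit to two SAPs, a re-derivation of the TEAE flag and possibly a re-run of the Part A AE tables. No new data are needed.

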## 15.2.2.2 Clinical Laboratory Tests

A by-subject listing will be provided including changes from baseline. Laboratory values that are outside the laboratory reference range will be flagged.

## 15.2.2.3 Vital Signs and ECGs

Observed and change from baseline values for vital sign and ECG parameters will be listed.

Values of potential clinical significance (e.g. change in QTcF ≥30ms from baseline) will be flagged and summarized by study visit.

# 15.2.3 Efficacy Analyses

The efficacy endpoints will be evaluated for the ITT Population.

Individual's data will be listed along with changes from baseline and percentage changes from baseline (where appropriate) for each visit. Data will be plotted by study day with each cohort and dose group being identifiable.

## 15.2.4 Pharmacokinetic Analyses

The PK parameters will be evaluated using the PK Population.

Individual concentration over time profile plots will be presented, with each cohort and dose group being identifiable. Both linear-linear and linear-log plots will be presented.

Where appropriate, steady-state PK parameters for APL-2 will be estimated from the individual serum concentrations over-time data, using actual sample times using a non-compartmental approach. Detailed PK analyses will include in the SAP.

## 15.2.5 Pharmacodynamic Analyses

The PD parameters will be evaluated using the PD Population.

Individual parameter over time profile plots will be presented, with each cohort and dose group being identifiable. Both changes from baseline and percentage changes from baseline will be presented.

# 15.2.6 Handling of Dropouts and/or Missing Data

No imputation of missing data for early terminations will be performed.

Where appropriate screening values may be used as baseline in the event of missing Day 1 measurements.

Missing dates/times will be reviewed on a case by case basis for potential imputations, but the original data will always be presented in data listings.

## 15.2.7 Other Data Analyses

Demographic data, baseline characteristics, physical examination, concomitant medication and medical history data will be listed by cohort and dose group. Current World Health Organization (WHO) and MedDRA coding dictionaries will be used for the concomitant medications and medical histories respectively.

# 15.3 Interim Analyses

One interim analysis is planed when all subjects enrolled in the study have completed Part A, the Core Study Phase (screening to day 336) or discontinued prior to Day 336.

# 15.4 Direct Access to Source Data/Documents

The PI must maintain, at all times, the primary records (i.e. source documents) of each subject's data for data verification. Examples of source documents are medical records, laboratory reports, study drug records, and eCRFs that are used as the source.

The PI will permit trial-related monitoring, audits, and inspections by the Sponsor and/or its' designee, IRB/IEC, and the regulatory agencies at any time during the study. The PI will ensure that the auditor is allowed direct access to the source data, medical records, eCRFs, and the Site's regulatory file for the study and any other pertinent information.

## 15.5 Quality Control and Quality Assurance

This study is to be performed in full compliance with the protocol, Good Clinical Practices (GCP), and applicable regulatory requirements. The PI, Sponsor and/or its' designee are responsible for ensuring that the study staff receive appropriate training on the protocol, study procedures and any other relevant information.

Quality assurance and quality control systems are implemented and maintained using written Investigative site, Sponsor and/or designee Standard Operating Procedures (SOPs) to ensure that the study is conducted and data are generated, documented (recorded), and reported in compliance with the protocol, GCP, and the applicable regulatory requirement(s) and local laws, rules, regulations.

Quality control (QC) checks will be applied at each stage of data handling (e.g. edit checks) to ensure that all data are reliable and have been processed correctly.

## 15.5.1 Monitoring

On-site monitoring will be performed by the Sponsor's designee for the duration of the study. The monitor will ensure that the study is conducted, recorded and reported in accordance with the protocol, SOPs, GCP, and the applicable regulatory requirements. The monitor will verify the accuracy and completeness of the eCRF entries, source documents, and other study-related records against each other. The PI will provide direct access to source data/documents for study-related monitoring. It is important that the PI and the staff are available at these visits. The monitor will record the date of each visit together with a summary of the status and progress of the study. Proposed actions will be documented in writing to the PI.

## 15.6 Ethics

# 15.6.1 Ethical Conduct of the Study

This research will be carried out in accordance with the protocol, applicable regulations, the ethical princliples set forth in the Declaration of Helsinki, and the ICH Harmonized Tripartite Guidance for Good Clinical Practice, E6, R1 (ICH GCP).

## 15.6.2 Institutional Review Board/Ethic Committee

The study protocol, any amendments to the protocol, informed consent form, the Investigator's Brochure, and other study specific information will be reviewed and approved by the IRB/IEC. The study will not be initiated until the IRB/IEC has approved the protocol or a modification thereof. All records pertaining to IRB/IEC submission and approval should be kept in the site's regulatory files and Sponsor's Trial Master File (TMF).

The IRB/IEC must be constituted and operate in accordance with all applicable regulatory requirements.

# 15.6.3 Subject Information and Consent

The PI or appropriate designee is responsible for obtaining an informed consent. A written informed consent, in compliance with ICH Guidance E6, must be obtained from each subject prior to screening and enrollment or performing any study related procedures.

The purpose of the study, the procedures to be carried out and the potential hazards will be described to the subjects in non-technical terms. The subject will be given sufficient time to consider the study's implications before deciding to participate in the study. The subject and/or legal guardian will be required to sign and date an Informed Consent Form (ICF) and will be

assured that they may withdraw from the study at any time without jeopardizing their medical care. The PI shall retain the original, signed informed consent for study participation in the subject's medical record and shall provide the subject and/or legal guardian with a copy of the signed consent.

Patients that live outside the United States who may wish to participate in this study for a period of time within the United States will be pre-consented by the PI and the local physician. The ICF (in local language) will be emailed to the subject's local physician. The ICF will be provided in advance to the patients to ensure adequate time is provided to ask questions and discuss any concerns. This procedure is completed to ensure patients understand the study, procedures, risks, and benefits, etc., before traveling to the United States for a screening visit. The patient will be consented by the PI over the phone/video with the local physician present on the call/video to aid in the discussion. Additional trained translators will be provided if needed to ensure subjects fully understand the protocol and can ask questions. The ICF will be signed by the patient, local physician, and PI once the patient arrives in the United States for the screening visit. The executed ICF will be stored locally at the PI's office. The PI may wish to re-consent the patient again once arriving to the United States.

If there are any changes/amendments to the approved protocol, which may directly affect the subject's decision to continue participation in the study, the ICF shall be amended to incorporate the changes to the protocol and the subject must re-sign the IRB/IEC approved amended ICF.

